**Efficacy Evaluation:**

Primary efficacy analyses will be conducted on the ITT (primary) and PP (supportive) populations. Secondary and supportive analyses will be conducted on the ITT population.

*Primary:*

Co-primary efficacy analyses include the absolute change from baseline in inflammatory and non-inflammatory lesions, and the dichotomized Evaluator's Global Severity Score. The pre-specified time point will be Week 12. All of the testing relating to the analysis of inflammatory and non-inflammatory lesions will use the methods introduced in Section 12.

*Secondary:*

Secondary efficacy endpoints include percent change in inflammatory and non-inflammatory lesion counts from baseline to Weeks 12, 8 and 4 and also percentage of subjects with at least a two grade improvement in the Evaluator's Global Severity Score from baseline to Week 12.

*Supportive:*

Additional supportive efficacy endpoints include percent change in inflammatory and non-inflammatory lesions counts from Baseline at Week 2, as well as percentage of subjects with at least a two grade improvement in the Evaluator's Global Severity Score from baseline at Weeks 2, 4, and 8.

**Safety Evaluation:**

All subjects who are confirmed to have used the study drug at least once will constitute the safety population. Safety will be evaluated by tabulations of adverse events (AEs), Cutaneous Tolerability Evaluations, vital signs/abbreviated physical exams, and safety labs.

Cutaneous Safety Evaluation scores (erythema, scaling, and hypo/hyper-pigmentation) and Tolerability (itching, burning, and stinging) will be presented with descriptive statistics at Baseline and at Weeks 2, 4, 8, and 12 for each treatment group. Frequencies and percentages for each outcome category will be included in these statistics. Mean values will be presented graphically by week and treatment group.

Vital signs, an abbreviated physical exam, and safety labs will be conducted on all subjects at specified visits. For pre-menses females and females of child-bearing potential (FOCBP), urine pregnancy testing and serum pregnancy testing will occur at specified visits. Changes from baseline in safety laboratory values and vital sign measurements will be summarized with descriptive statistics for each treatment group at all applicable study visits. Shift tables will be presented for changes in safety laboratory values collected at Baseline and Week 12 Visits. Normal ranges established by the central laboratory will be used to determine the shifts. A listing of all out-of-range laboratory test results at any assessment time point will also be provided.

Determination of clinical significance for all out-of-range laboratory values will be made by each investigator and included in the listing. In addition, a listing of all clinically significant laboratory test results will be provided.

All recorded prior and concomitant medications will be classified based on terminology from the WHO Drug Dictionary. Therapies and medications data will be presented in the data listings.

All adverse events occurring during the study will be recorded and classified on the basis of MedDRA terminology. Descriptions of AEs will include the date of onset, the date the AE ended, the severity of the AE, the relationship to study drug, the action taken regarding study drug usage, the action taken regarding to treat the AE, and the outcome. Adverse events will be summarized by treatment group and severity. Each subject will be counted only once within a system organ class or a preferred term by using the adverse events with the highest severity within each category.

Adverse events will be summarized by treatment group and relationship to study drug. Each subject will be counted only once within a system organ class or a preferred term by using the adverse events with the greatest relationship within each category.

Comparisons among treatment groups will be made by tabulating the frequency of subjects with one or more AEs (classified into MedDRA terms) during the study. The Fisher's Exact test will be used to compare the percentage of subjects in each treatment group who report any adverse event at a significance level of 0.05. The specific system organ classes and preferred terms analyzed will be those that are reported by at least one percent of the subjects in any treatment group.

All information pertaining to AEs noted during the study will be listed by subject, detailing verbatim given by the investigator, preferred term, system organ class, start date, stop date, severity, actions taken, and drug relatedness. The AE onset will also be shown relative (in number of days) to the day of initial dose of the randomized study drug.

Serious adverse events (SAEs) will be tabulated by subject within treatment groups.

In addition, a list of subjects who discontinued from the study and a list of subjects who experienced SAEs will also be provided.

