## 8 Selection and Withdrawal of Subjects

### 8.1 Subject Inclusion Criteria

Subjects meeting all of the following criteria will be eligible for study entry:

1. Male or female at least 9 years of age and older;
2. Written and verbal informed consent must be obtained. Subjects less than age of consent must sign an assent for the study and a parent or a legal guardian must sign the informed consent (if subject reaches age of consent during the study they should be re-consented at the next study visit);
3. Subject must have a score of 3 (moderate) or 4 (severe) on the Evaluator's Global Severity Score (EGSS) assessment at the baseline visit;
4. Subjects with facial acne inflammatory lesion (papules, pustules, and nodules) count no less than 20 but no more than 50;
5. Subjects with facial acne non-inflammatory lesion (open and closed comedones) count no less than 25 but no more than 100;
6. Subjects with two or fewer facial nodules;
7. Females of childbearing potential and females who are pre-menses must be willing to practice effective contraception for the duration of the study. (Effective contraception is defined as stabilized on oral contraceptive for at least 3 months, IUD, condom with spermicidal, diaphragm with spermicidal, implant, Nuvaring, injection, transdermal patch, abstinence or sterile partner.) Females on hormonal contraceptive must have taken the same type for at least three months prior to entering the study and must not change type during the study. Those who have used hormonal contraception in the past must have discontinued usage at least three months prior to the start of the study. Women who use birth control for acne control only should be excluded.
8. Pre-menses females and females of childbearing potential must have a negative urine pregnancy test at the screening and baseline visits;
9. Subjects must be willing to comply with study instructions and return to the clinic for required visits. Subjects under the age of consent must be accompanied by the parent or legal guardian at the time of assent/consent signing;
10. If a cleanser, moisturizer or sunscreen is needed during the study, subjects must be willing to use only allowed cleansers, moisturizers, sunscreens, or

---

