### 11.2.2 Lesion Counts

The facial area lesion counts will be taken from the subject's face (including the nose). The lesion count groups will be inflammatory and non-inflammatory. Facial inflammatory lesions (pustules, papules, and nodules) will be counted as follows: pustules and papules will be counted and recorded together, not separately; nodular lesions will be counted and recorded separately. Non-inflammatory lesions (open and closed comedones) will be counted and recorded together. The lesions counts will be collected at each visit and/or upon discontinuation. The following are definitions of each lesion type counted:

*Inflammatory lesions* are defined as follows:

Papule: An erythematous, raised, palpable lesion less than 5 mm in diameter  
 Pustule: An erythematous, raised, likely palpable lesion containing white exudate or pus less than 5 mm in diameter  
 Nodule: A deep-seated, erythematous, firm lesion greater than 5 mm in diameter

*Non-inflammatory lesions* are defined as follows:

Open comedone (blackhead): A widely dilated sebaceous follicle plugged with darkly pigmented sebum  
 Closed comedone (whitehead): A small, closed sebaceous follicle distended with sebum, with a white appearance

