### 11.3.1 Cutaneous Safety Evaluations

Cutaneous safety will be evaluated through assessment of scaling, erythema, hypo-pigmentation and hyper-pigmentation at the drug-application site at the time of the visit. Cutaneous tolerability will be evaluated through assessment of selected local signs and symptoms at the drug-application site: itching, burning and stinging, as an average since the last visit.

Cutaneous safety and tolerability signs and symptoms that result in the subject requiring a concomitant therapy, interruption of treatment, or discontinuation from the study, will be reported as an AE.

(Note: To be assessed by the evaluator at the time of the study visit.)

*Scaling:*

0 – None	No scaling
1 – Mild	Barely perceptible, fine scales present on limited areas of the face
2 – Moderate	Fine scale generalized to all areas of the face
3 – Severe	Scaling and peeling of skin over all areas of the face

*Erythema:*

0 – None	No evidence of erythema present
1 – Mild	Slight pink coloration
2 – Moderate	Definite redness
3 – Severe	Marked erythema, bright red to dusky dark red in color

*Hypo-pigmentation:*

0 – None	No evidence
1 – Mild	Slight, barely perceptible
2 – Moderate	Definite, evident
3 – Severe	Marked, prominent

*Hyper-pigmentation:*

0 – None	No evidence
1 – Mild	Slight, barely perceptible
2 – Moderate	Definite, evident
3 – Severe	Marked, prominent

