## **12.2 Assessment of Safety**

Safety will be evaluated by tabulations of adverse events (AEs), Cutaneous Safety Evaluation, and Tolerability Evaluations. Cutaneous Safety Evaluation scores (erythema, scaling, and hypo/hyper-pigmentation) and Tolerability (itching, burning, and stinging) will be presented with descriptive statistics at Baseline and at Weeks 2, 4, 8, and 12 for each treatment group.

Frequencies and percentages for each outcome category will be included in these statistics. Mean values will be presented graphically by week and treatment group.

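### Cutaneous scores get no within-subject comparison with Baseline, so by-visit tables can understate erythema (and possibly pigmentation) worsening that is too mild to require an AE report

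*Combined protocol and SAP*

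**What the plan says.** The synopsis (Safety Evaluation) and Section 12.2 plan the same summary for erythema, scaling, pigmentation, itching, burning and stinging. The scores "will be presented with descriptive statistics at Baseline and at Weeks 2, 4, 8, and 12 for each treatment group". Section 12.2 adds: "Frequencies and percentages for each outcome category will be included in these statistics". It also says: "Mean values will be presented graphically by week and treatment group". Nothing else is planned for these scores in this text.

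Other safety data are handled differently. The synopsis says: "Changes from baseline in safety laboratory values and vital sign measurements will be summarized with descriptive statistics". For laboratory data it goes further: "Shift tables will be presented for changes in safety laboratory values collected at Baseline and Week 12 Visits". Sections 12.2.2 and 12.2.3 repeat these plans in substance.

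The data for a within-subject comparison exist. Table 1 schedules the cutaneous evaluations at Baseline and at every later visit, and Section 11.1.2 places the first application after all Baseline assessments. Section 11.3.1 has the evaluator grade erythema, scaling and pigmentation "at the drug-application site at the time of the visit". The erythema grades describe color only, from none to bright or dusky red.

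**The concern.** Safety and tolerability are part of the primary objective (Section 6), and Section 5 names erythema and scaling among the known side effects of topical retinoids. The erythema score can carry two opposite effects of the drug:

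- **Acne contributes redness.** Section 11.2.2 defines the first inflammatory lesion as "Papule: An erythematous, raised, palpable lesion less than 5 mm in diameter", and pustules are likewise described as erythematous. Section 8.1 requires an inflammatory lesion "count no less than 20 but no more than 50". The erythema grades do not tell the evaluator to disregard lesional redness.
- **Efficacy removes redness.** The Almost Clear grade in Table 4 allows only resolving papules that are no longer pink or red. Clearing is expected to differ by arm, so the vehicle comparison does not remove the offset.
- **Pigmentation may be affected too.** The same grade allows resolving papules to be hyperpigmented.

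A table of group totals at each visit shows only the net of those who improved and those who worsened. If more subjects clear on active, the active arm's excess of newly irritated subjects looks smaller than it is.

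**Working it through.** The plan states no figure for these scores, so there is none to reproduce. From the documents I take 300 subjects per arm and the Week 12 EGSS success rates of 26.6% v 14.3% (both Section 12.8.2). Every other rate below is an assumption.

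**1. What fixed totals allow.** Suppose 30% of an arm have moderate or severe erythema at Baseline and 30% at a later visit, in the same subjects. The number who moved up then equals the number who moved down. The share who worsened from none/mild to moderate/severe can be anything from 0% to min(30%, 70%) = 30%. This shows what the totals leave open. It is not evidence about this trial.

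**2. How much of a real difference the visit table shows.** For one arm, let b be the share moderate or severe at Baseline, c the proportion of those who clear to none/mild, and i the share of all subjects newly moved from none/mild to moderate/severe.

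- Visit share = b − b·c + i
- Share worsened = i
- Difference in visit shares, active minus vehicle = (i_A − i_V) − b(c_A − c_V)

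The last term is the offset. Take b = 30% in both arms, i_A = 12% and i_V = 2%. The share worsened is then 12% v 2%, a difference of 10 points. Its Wald 95% CI half-width is 1.96 × √(0.12×0.88/300 + 0.02×0.98/300) = 4.0 points, giving 6 to 14.

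| Assumed clearing, active v vehicle | Active visit share | Vehicle visit share | Difference (95% CI), points |
|---|---|---|---|
| 50% v 25% | 30 − 15 + 12 = 27.0% | 30 − 7.5 + 2 = 24.5% | 2.5 (−4.5 to 9.5) |
| 26.6% v 14.3% (EGSS success as a rough proxy) | 30 − 7.98 + 12 = 34.0% | 30 − 4.29 + 2 = 27.7% | 6.3 (−1.1 to 13.7) |
| None yet (possible at Week 2) | 30 + 12 = 42% | 30 + 2 = 32% | 10 (2.3 to 17.7) |

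The offset is 30% × 25 = 7.5 points in the first row, 30% × 12.3 = 3.7 in the second and 0 in the third. For the 10 points to cancel completely at b = 30%, clearing would have to differ by 10/0.30 = 33.3 points.

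**3. The same point on the full 0–3 scale.** These are assumed counts. Rows are Baseline grade 0 to 3 and columns are visit grade 0 to 3.

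- Active: (60, 25, 5, 0), (25, 70, 20, 5), (5, 20, 45, 5), (0, 5, 5, 5). Counts above the diagonal sum to 60, so 60/300 = 20.0% worsened.
- Vehicle: (80, 10, 0, 0), (10, 100, 10, 0), (0, 10, 60, 5), (0, 0, 5, 10). Counts above the diagonal sum to 25, so 25/300 = 8.3% worsened.

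In both arms the totals are 90/120/75/15 at Baseline and again at the visit, with mean (120 + 2×75 + 3×15)/300 = 1.05 each time. The planned percentages and means would show no difference between arms or over time, although 20.0% v 8.3% worsened (Fisher p = 0.00006).

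**4. Which remedies work.** Mean change from Baseline does not help. With the same subjects at both visits it equals the difference of the visit means, here 0.00. A worst-grade table alone does not help either, because a subject who starts at grade 2 from acne counts as moderate with no drug effect. The comparison has to be with the subject's own Baseline grade.

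**The case against.** The case against is substantial, and much of it stands as a limit on the point.

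- **Scope.** A reader might infer that all seven scores are affected by netting. The documents do not support that. The lesion definitions do not mention scaling, itching, burning or stinging, so clearing acne has no stated route to lowering those scores.
- **Adverse events.** A reader might infer that drug irritation disappears from the safety report. Under the synopsis and Sections 11.3.1 and 11.4.2, signs or symptoms that need other therapy, a break in treatment or withdrawal are reported as AEs, and Section 12.2.1 tabulates these by arm with a Fisher test. The general AE definition in Section 11.4.1 also covers signs that appear or worsen, so some milder irritation may be recorded. Irritation below the specific threshold is not required to reach the AE tables.
- **Baseline is not ignored.** It is tabulated by arm beside each later visit, and the vehicle arm is randomized. The visit comparison is a valid estimate of the net effect on facial redness. A large or early effect would still show, and Week 2 is a planned column.
- **The numbers are assumed.** The 50% v 25% clearing rates are favorable to the concern. The only responder rates in the documents, used as a proxy, leave 6.3 of the 10 points visible. It is also an inference that evaluators will score lesional redness as erythema.
- **The remedy is imperfect.** On a single face, clearing followed by irritation reads as unchanged, and an acne flare reads as worsening. A shift table still prevents one subject's clearing from canceling another's worsening, which the planned tables cannot do.
- **A separate SAP.** Section 12 promises one, to be final before unblinding, and it could add such tables. The present text does not, and it is the plan as it stands.

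**Conclusion.** The point holds in a limited form. The plan gives the cutaneous scores no within-subject comparison with Baseline. For erythema, and possibly pigmentation, treatment-related worsening below the AE-reporting threshold can therefore be understated in the visit tables. For the other four scores the loss is only within-subject detail.

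The size cannot be established from the documents. Under the assumed rates, a true 10-point difference in subjects newly irritated shows as 2.5 to 10 points, depending on how far acne redness has cleared in each arm. This rests on evaluators including lesional redness in the erythema grade and on the same subjects being seen at both visits.

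A reader might go further and conclude that the active arm will look no more irritating than vehicle. The documents do not support that: it requires a large difference in clearing, and they give no cutaneous data from which to judge one. The change is still worth making, because tolerability is in the primary objective and the Baseline scores are already collected.

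**What to change.** In Section 12.2 and the synopsis, keep the planned tables and plots, and add by arm and post-baseline visit:

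- a shift table of Baseline grade against visit grade;
- the number and percent of subjects at least one grade worse than their own Baseline;
- the number and percent who worsened from none/mild to moderate or severe;
- the arm difference with a 95% CI for both percentages.

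The priority is erythema and the two pigmentation scores. The same table shell can serve scaling, itching, burning and stinging. A note under the erythema table should say that the score does not distinguish lesional redness from irritation.

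The cost is some plan wording and a few extra tables from data already scheduled, with no new assessment. The added tables still cannot separate irritation from acne clearing or flare on the same face.

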#### **Subject Self-Assessment**

Subjects will be asked to complete the Acne-Specific Quality of Life Questionnaire during the study. Inferential statistical analysis will not be performed on the questionnaire; the subjective responses will be compared between treatment groups for trends.

This study will be performed in compliance with GCP including the archiving of essential study documents. This protocol follows guidelines outlined by the International Conference on Harmonization (ICH). All data furnished to the investigator and his/her staff, and all data obtained through this study, will be regarded as confidential and proprietary in nature and will not be disclosed to any third party, except for the United States Food and Drug Administration or other regulatory body, without written consent from the sponsor.

## 4 List of Abbreviations and Definitions of Terms

Abbreviation or Specialist Term	Definition or Explanation
AE	Adverse event
ANCOVA	Analysis of Covariance
CRF	Case Report Form
CRO	Contract Research Organization
eCRF	Electronic Case Report Form
EGSS	Evaluator's Global Severity Score
ET	Early termination
FDA	United States Food and Drug Administration
FOCBP	Female of Childbearing Potential
g	Gram
GCP	Good Clinical Practice
ICH	International Conference on Harmonization
IEC	Independent Ethics Committee
IRB	Institutional Review Board
ITT	Intent-to-treat
IWRS	Interactive Web Response System
LED	Light Emitting Diode
MCMC	Markov Chain Monte Carlo
MedDRA	Medical Dictionary for Regulatory Affairs
mL	Milliliter
OTC	Over-the-counter
PDT	Photodynamic Therapy
PP	Per protocol
QoL	Quality of Life
SAE	Serious adverse event
UPT	Urine Pregnancy Test
WHO	World Health Organization

In this protocol, “sponsor duties” refer to responsibilities that will be performed by the sponsor, the sponsor’s designee, or the sponsor’s designated contract research organization. In this protocol, “investigator” refers to the principal investigator or his/her designee, who is responsible for performing the study procedures and assessments.

## 5 Introduction

Acne is a very common disorder of sebaceous follicles that usually begins at the time of the sharp increase in androgen production occurring in adolescence [1]. The disease is most prevalent amongst teenagers, but it does occur later in life, particularly in the third and fourth decade. The pathogenesis is complex and involves an androgen-stimulated increase in sebum production, associated with follicular hyperkeratinization and obstruction of the sebaceous follicles. This results in abnormal desquamation of the follicular epithelium, and is associated with bacterial proliferation (especially *Propionibacterium acnes* (*P. acnes*)) and chronic inflammation associated with acne. These changes in acne subjects result in enlarged sebaceous glands; obstruction of the follicular canal with associated sebum retention and distention of the follicle by tightly packed horny cells that lead to the formation clinical inflammatory lesions including superficial pustules such as comedones (popularly known as “blackheads” or “whiteheads”); and more deeply located papules, nodules and cysts [1]. The areas most affected by the disease include the pilosebaceous follicles of the head and upper trunk, where the sebaceous glands are particularly active [2].

Currently, therapeutic treatment of acne is directed against 3 principal pathogenic factors of the disease, including the bacterial colonization of follicles, the hypersecretion of the sebaceous gland, and intrafollicular hypercornification that induces follicular obstruction. Effective treatment directed against the colonization of bacteria (*P. acnes*) in follicles has made use of anti-infectives such as topical benzoyl peroxide (2.5%-10%), clindamycin, and erythromycin and systemic tetracyclines; however, known disadvantages to this treatment modality include irritation and limited use due to pathogen resistance [2-5]. Effective treatment directed towards inhibiting sebaceous gland activity has included oral corticosteroids, spironolactone, and isotretinoin in addition to anti-androgens (eg, cyproterone acetate). Known disadvantages to this treatment modality include being limited to use in females (anti-androgens), and limited to short term use for safety (oral corticosteroids). Finally, effective treatment directed against intrafollicular hypercornification has made use of retinoids such as oral isotretinoin and topical tretinoin or isotretinoin to regulate the intrafollicular keratinization process, inhibiting follicular hyperkeratinization and follicular obstruction [6]. In general, the known usefulness of oral retinoids (ie, oral isotretinoin) is limited by their side effects, which range from relatively minor effects (eg, dryness of mucosa and skin, skin irritation, and skin scaling) to major toxicity syndromes (reversible hair loss, bone toxicity and teratogenicity) and may include varying degrees of symptoms associated with hypervitaminosis A syndrome [2, 7, 8]. Likewise, the efficacy of topical retinoids such as tretinoin or isotretinoin may be limited by the known side effects, which include significant erythema, dryness, peeling, scaling, and irritation [9].

Tretinoin and benzoyl peroxide are retinoid prodrugs that activate 3 members of the retinoid acid receptor (RAR) nuclear receptors (RAR $\alpha$ , RAR $\beta$ , and RAR $\gamma$ ), which act to modify gene expression, subsequent protein synthesis, and epithelial cell growth and differentiation. Tretinoin and benzoyl peroxide show a relative selectivity for RAR $\beta$ , and RAR $\gamma$ . It has not been established, however, whether the clinical effects of tretinoin and benzoyl peroxide are mediated through activation of RARs, other mechanisms, or both. Although the mechanism of action for tretinoin and benzoyl peroxide in the treatment of acne is unknown, the drug's antihyperproliferative, normalizing-of-differentiation, and anti-inflammatory effects may be related to the observed efficacy.

IDP-120 Gel is packaged in a dual-chamber airless pump, with each active gel contained in a separate cartridge. Specifically, one cartridge is filled with tretinoin (0.1%) gel, while the other is filled with BPO (5%) gel. The gels will be mixed (outside of the pump) immediately prior to topical application on affected skin. When combined, the gels dispensed from the pump will have a concentration of tretinoin, 0.05% (w/w) and BPO, 2.5% (w/w). This proposed product is the first gel formulation developed for tretinoin and benzoyl peroxide and will be evaluated for safety and effectiveness in treating acne vulgaris.

